**Grünenthal**  
Confidential

Protocol KF7013-03  
including Amendment 04

Page 14 of 128  
DMS version 5.0  
17 Nov 2017

- 
- j) All baseline measurements (including blood sampling for hematology and clinical chemistry, urinalysis, ECG, vital signs, and physical examination) must be completed and results available before the start of the first infusion of IMP. Investigational medicinal product must be diluted in 500 mL saline and administered by slow intravenous infusion (the infusion time must be at least 240 minutes [up to a maximum of 260 minutes]).
- k) After Visit 1, record any changes from the previous visit.
- l) At Visit 2 through Visit 5, vital signs will be taken once at least 15 minutes before the infusion and once at least 15 minutes after the infusion. Body weight will be included as a vital sign and will be measured at all visits (only once at Visit 2 to Visit 5, prior to the infusion).
- m) At Visit 2 through Visit 5, triplicate ECGs will be recorded once at least 15 minutes before the infusion and once at least 15 minutes after the infusion. A triplicate ECG will be recorded for all other visits.
- n) Subjects should be queried for any events occurring since the previous visit; any events noted at Visit 1 should be documented as medical history or as part of physical examination results.
- o) The diagnosis of CRPS must be confirmed using the tablet computer at Visit 1 according to the clinical diagnostic criteria recommended by the IASP (Budapest clinical criteria) (Section 12.2.3.1). The number of signs and symptoms of CRPS at Visit 2, and Visit 7 to Visit 11, inclusive, will be summed for determination of the CRPS Severity Score (Section 12.4.8).
- p) At Visit 2 through Visit 5, urine collection must be performed prior to infusion. In addition to the sample for central safety laboratory analysis, a local dipstick evaluation for determination of urinary albumin creatinine ratio must be performed prior to the start of infusion.
- r) C-terminal telopeptide of type I collagen (CTX), bone alkaline phosphatase (BAP), and PINP (procollagen type I amino-terminal propeptide).
- s) For women of child-bearing potential, a negative urine pregnancy test result must be obtained prior to each infusion. For subjects who discontinue the trial prior to completion, pregnancy testing should be performed at the Early Termination Visit (whose procedures are identical to Visit 11).
- t) The subject card is to be returned at the final visit or at the Early Termination Visit in the case of early discontinuation from the trial.
- u) It is planned to perform bone densitometry (DXA) and MRI in a subset of 30 subjects.
- v) A single bone biopsy will be obtained from the iliac crest, following tetracycline double-labeling, in a subset of subjects. The biopsy should be scheduled to be performed 26 weeks after the first administration of IMP. It is planned to obtain approximately 15 evaluable bone biopsy samples from approximately 20 subjects.
- w) At US sites only.
- x) For US subjects undergoing bone biopsy only.

$\beta$ -HCG = beta-human chorionic gonadotropin, BPI = Brief Pain Inventory, CES-D = Center for Epidemiological Studies Depression Scale, CRPS = complex regional pain syndrome, DXA = dual-energy X-ray absorptiometry, ECG = electrocardiogram, eGFR = estimated glomerular filtration rate, EQ-5D-5L = EuroQol-5 dimension 5 level, IASP = International Association for the Study of Pain, IMP = investigational medicinal product, MRI = magnetic resonance imaging, NRS = numerical rating scale, PASS = Pain Anxiety Symptom Scale, PDI = Pain Disability Index, PGIC = Patient Global Impression of Change, WPAI = Work Productivity and Activity Impairment Questionnaire.

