#### **11.1.1.1 Visit 1 (Day -60 to Day -1)**

The following evaluations will be performed:

- Obtain written informed consent.
- Record demographic data.
- Record medical history (includes history of CRPS; for further details, see Section 1.6).
- The diagnosis of CRPS must be confirmed using the tablet computer at Visit 1 according to the clinical diagnostic criteria recommended by the IASP (Budapest clinical criteria) (for further details, see Section 12.2.3.1).
- Record dental history (for further details, see Section 1.6).
- Dispense calcium and vitamin D supplements (for further details, see Section 1.6).
- Record prior medications and therapies.
- Review inclusion/exclusion criteria.
- Record physical examination outcome.
- Record vital signs.
- Record triplicate 12-lead ECG.
- Record concomitant medications and therapies.
- Ask the subject to complete pain intensity assessments.
- Take blood for safety laboratory.
- Collect urine for central safety laboratory urinalysis.
- Perform a urine  $\beta$ -HCG pregnancy test (for women of child-bearing potential).
- Perform urine drugs of abuse testing.
- Provide subject trial card.
- Perform bone imaging (DXA and MRI will be performed in a subset of approximately 30 subjects [from US sites only]).
- Record adverse events (any events noted should be documented as medical history or as part of physical examination results).

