## **12.2.4 Other baseline characteristics**

### **12.2.4.1 Physical examination**

Physical examination should include assessments of the general condition, skin, eyes, ears, nose and throat, mouth (including teeth and gums), head, neck, and thyroid, heart, lung, chest, abdomen, kidneys, liver, lymphatic, musculoskeletal, and neurological systems.

Prior to allocation to treatment, any clinically relevant findings from the physical examination will be documented as part of the medical history.

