### **12.3.1 Adverse events**

Adverse events will be documented from the time of enrollment (i.e., the time the informed consent form is signed) up to the time of the last protocol scheduled contact, i.e., date of last visit/contact (can be a phone call, e.g., in case of withdrawal).

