#### **Definition of adverse events**

An adverse event is any untoward medical occurrence in a subject enrolled in a clinical trial. An adverse event can therefore be any unfavorable and unintended sign (e.g., an abnormal laboratory finding), symptom, or disease temporally associated with the use of a medicinal product, whether or not considered related to the medicinal product.

Pre-existing diseases or conditions occurring before enrollment are not considered to be adverse events unless there is an untoward change in intensity, frequency, or quality after enrollment.

Lack of efficacy, as such, is not considered to be an adverse event while its consequences (e.g., deterioration of the treated disease) are considered to be an adverse event.

A newly diagnosed pregnancy of an enrolled female subject will not be considered an adverse event itself unless it is suspected that the trial treatment interacted with a contraceptive method. In this case, the pregnancy will be considered an adverse event. A congenital anomaly as an outcome of a pregnancy will be considered a serious adverse event (SAE).

All newly diagnosed pregnancies of enrolled female subjects must be reported to the sponsor's Drug Safety Department within 24 hours after first knowledge. These pregnancies will be documented using a pregnancy reporting form with all available information provided and followed up to determine the outcome post parturition.

For newly diagnosed pregnancies of partners of enrolled subjects, a reasonable attempt (i.e., due diligence) must be made to report the pregnancy to the sponsor's Drug Safety Department within 24 hours after first knowledge.

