**Notification of serious adverse events**

All SAEs (including death, irrespective of cause) during the trial, regardless of their relationship to IMP, must be reported as soon as possible but no later than 24 hours after learning of the event. Before any trial-related procedure is performed, the trial site must be provided with contact details at the sponsor's Drug Safety Department for this reporting.

---

The investigator must submit a report, called a safety reporting form, which includes a description of the event, the therapy instituted, and trial procedures. The following information should be communicated with the first notification of an SAE:

- Trial identifier
- Subject's identifier.
- Subject's date/year of birth (if available, see local data protection requirements) or age (at adverse event onset).
- Subject's sex.
- First administration of IMP (date and time, if available).
- Last administration of IMP (date and time, if available).
- Adverse event verbatim term (specific diagnosis, if possible).
- Adverse event onset (date and time, if available).
- A brief description of the event, the course, and the countermeasures taken.
- Intensity
- Seriousness criterion.
- Outcome
- Concomitant medication at onset of the event and whether one of the concomitant medications is also suspected to have caused the event.
- Relevant history/pre-existing medical conditions.
- Investigator's assessment of the relationship to IMP(s).

All additional information concerning the adverse event until trial termination or definite outcome must be communicated per follow-up report without delay.

The immediate and follow-up reports must only identify the subjects using the unique subject identifier.

The investigator must comply with applicable regulatory requirement(s) related to the reporting of SAEs to the regulatory authorities and the relevant IECs or IRBs.

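### Protocol rules for Visit 1 events and pre-allocation examination findings file them as history whatever their onset, contradicting the rule that adverse events are recorded from consent

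*Protocol*

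**What the plan says.** **The general rule.** Protocol 12.3.1 says: "Adverse events will be documented from the time of enrollment (i.e., the time the informed consent form is signed". The definition of adverse events in the same section gives one exemption: "Pre-existing diseases or conditions occurring before enrollment are not considered to be adverse events unless there is an untoward change". Protocol 3.2 defines enrolled subjects as those who have signed consent, so enrollment and consent are the same moment.

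**The Visit 1 rule.** Footnote n in Protocol 1.6 says that "any events noted at Visit 1 should be documented as medical history or as part of physical examination results". The Visit 1 procedure list in 11.1.1.1 has the same instruction inside its adverse event item: "Record adverse events (any events noted should be documented as medical history or as part of physical examination results".

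**The examination rule.** Protocol 12.2.4.1 says: "Prior to allocation to treatment, any clinically relevant findings from the physical examination will be documented as part of the medical history". Its counterpart, 12.3.6, makes clinically relevant examination changes adverse events only once treatment has been allocated.

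**Serious events.** The notification subsection of 12.3.1 says: "All SAEs (including death, irrespective of cause) during the trial, regardless of their relationship to IMP, must be reported as soon as possible". The limit is 24 hours after learning of the event.

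**Planned use of the data.** SAP 8.2.2 runs the pre-treatment period from consent to first dose. SAP 15.1.1 tabulates pre-treatment adverse events, and serious ones separately, for all enrolled subjects.

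**The concern.** Two sets of instructions cover the same stretch of time and divide it differently. The general rule divides it at consent, by onset. The Visit 1 rule divides it by the visit at which the event is noted, and the examination rule divides it at allocation. Neither asks when the event began. A site that follows the specific instruction will put some events that meet the protocol's own definition of an adverse event into medical history or the examination record. Another site may follow 12.3.1 and enter the same event as an adverse event.

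What is at stake is the completeness of the SAP 15.1.1 pre-treatment tables, and their consistency between sites. There is also a secondary risk. The seriousness question is part of the adverse event entry (Protocol 12.3.1, documentation of adverse events). An event filed as history may never be put to that question.

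**Working it through.** No arithmetic beyond one interval applies. The check is to follow each kind of event through the rules.

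1. **Event starting during Visit 1, after signature.** Protocol 4.2 requires consent before any trial-related procedure, and 11.1.1.1 lists consent first. Blood sampling, ECGs, supplement dispensing and, in a subset, imaging also belong to Visit 1. An untoward event during these procedures starts after enrollment, so 12.3.1 makes it an adverse event and the exemption does not reach it. Footnote n and 11.1.1.1 send it to history or examination results. The rules conflict.

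2. **New clinically relevant finding at the Visit 2 pre-dose examination.** The Visit 2 examination records what has changed since the last visit (1.6 footnote k; 11.1.2.1). A new change therefore arose after the Visit 1 examination, and so after consent. Visit 1 may fall on Day -60. The SAP counts a date before Day 1 as the date minus Day 1 (20.1.1.4), so Day -60 is 60 days before Visit 2, and the finding may come up to 60 days after consent. It is an adverse event under 12.3.1. Section 12.2.4.1 sends it to history, and 12.3.6 does not yet apply because allocation has not happened. The rules conflict.

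3. **Other event between Visit 1 and first dose.** Footnote n also says "Subjects should be queried for any events occurring since the previous visit", and 11.1.2.1 records adverse events at Visit 2, including those reported before the infusion. Spontaneous reports are documented at any time (12.3.1). The intensity subsection of 12.3.1 provides for adverse events that begin in the enrollment period and worsen after dosing, so the protocol expects pre-dose adverse events to exist. There is no conflict.

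4. **Serious event before first dose.** The notification rule covers all serious events during the trial and has no exception for Visit 1 or the time before dosing. It applies whichever form the event is filed on.

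5. **Effect on outputs.** Events of types 1 and 2 fall inside the SAP 8.2.2 pre-treatment period. If filed as history, they would not reach the SAP 15.1.1 pre-treatment tables. Treatment-emergent events start after first dose (SAP 15.1), so the primary endpoint (SAP 15.5) does not count events of either type.

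**The case against.** The strongest reply is that footnote n was never meant to cover post-consent events. Visit 1 has no previous visit, so what a subject reports there is ordinarily history from before consent, which 12.3.1 also excludes. The footnote says should, which Protocol 3.2 defines as recommended rather than mandatory. Clinically relevant abnormal values in the safety data must be recorded as adverse events (12.3). Examinations before allocation are scheduled only at Visits 1 and 2, so few findings can be affected.

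Much of this stands. It confines the Visit 1 conflict to events that start between signature and the end of that visit, and it makes the probable intent clear. It does not remove the conflict, because the text makes no distinction by onset. The argument from should does not reach 12.2.4.1, which is worded as a plain directive.

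A reader might go further and infer that pre-treatment serious events escape 24-hour reporting. The documents do not support that: the notification rule is a separate must with no pre-dose exception, and recording an event as history does not cancel it. What remains is the possibility that a misfiled event is never assessed for seriousness.

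A reader might also infer that adverse events across the whole enrollment period of up to 60 days go unrecorded. They do not, because most are picked up by the Visit 2 query. That safeguard is weaker for subjects who fail enrollment, who may have no Visit 2 but belong to the all-enrolled tables. Even for them, spontaneous reports are documented.

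**Conclusion.** The contradiction is real and narrow. Footnote n and 11.1.1.1, and separately 12.2.4.1 with 12.3.6, cannot be followed together with 12.3.1 for two kinds of event: those starting after consent during Visit 1, and clinically relevant examination findings that are new at Visit 2 before dosing. Where sites follow the specific instructions, the SAP 15.1.1 pre-treatment tables will be too low.

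The number of affected events is not in the documents and cannot be derived from them; it is probably small. The tables are descriptive and no inferential test is planned (Protocol 1.5). The primary endpoint is not affected, and the duty to report serious events is intact. This is a wording inconsistency worth correcting, not a threat to the trial's conclusions. The verdict assumes that sites read the instructions literally. If training or CRF completion guidance already divides events by onset, the practical effect is smaller still.

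**What to change.** Reconcile Protocol 1.6 footnote n, 11.1.1.1, 12.2.4.1 and 12.3.6 with 12.3.1, using onset relative to consent as the only dividing line:

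- Conditions and clinically relevant findings with onset before signature of consent are medical history.
- Events and clinically relevant examination findings with onset, or untoward worsening, after signature are adverse events. This includes those arising during Visit 1 and those found before allocation.
- Assessment for seriousness, and the 24-hour rule, run from signature of consent.

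Three details matter. The worsening clause keeps the change consistent with the definition in 12.3.1. The clinically relevant qualifier keeps trivial examination findings out. Section 12.3.6 has to change together with 12.2.4.1, or the contradiction only moves. The SAP needs no change, because its pre-treatment period already starts at consent.

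The cost is a few lines of wording in four places and a few more pre-treatment adverse event entries.

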### 3 LIST OF ABBREVIATIONS AND DEFINITION OF TERMS

#### 3.1 Abbreviations

Abbreviation	Explanation
ACR	Albumin creatinine ratio
β-HCG	Beta-human chorionic gonadotropin
BAP	Bone alkaline phosphatase
BMD	Bone mineral density
BPI	Brief Pain Inventory
CES-D	Center for Epidemiological Studies Depression Scale
CKD-EPI	Chronic Kidney Disease Epidemiology Collaboration
CRF	Case report form
CRO	Contract research organization
CRPS(-I)(-II)	Complex regional pain syndrome (Type I) (Type II)
CTX	C-terminal telopeptide of type I collagen
DMC	Data monitoring committee
DXA	Dual-energy X-ray absorptiometry
ECG	Electrocardiogram
EFPIA	European Federation of Pharmaceutical Industries and Associations
eGFR	Estimated glomerular filtration rate
EQ-5D-5L	EuroQoL-5 dimension 5 level
FDA	Food and Drug Administration
GCP	Good clinical practice
IASP	International Association for the Study of Pain
IEC	Independent ethics committee
IMMPACT	Initiative on Methods, Measurement, and Pain Assessment in Clinical Trials
IMP	Investigational medicinal product
IRB	Institutional review board
IRT	Interactive response technology
MDMA	3,4-methylenedioxy methamphetamine
MedDRA	Medical Dictionary for Regulatory Activities
MMRM	Mixed-effects model for repeated measurements
MRI	Magnetic resonance imaging
NRS	Numerical rating scale
NSAID	Non-steroidal anti-inflammatory drug
ONJ	Osteonecrosis of the jaw
PASS	Pain Anxiety Symptom Scale
PDI	Pain Disability Index
PGIC	Patient Global Impression of Change

Abbreviation	Explanation
PINP	Procollagen type I amino-terminal propeptide
QTcB	QT interval (corrected according to Bazett's formula)
QTcF	QT interval (corrected according to Fridericia's formula)
ROIs	Regions of interest
SAE	Serious adverse event
SOP	Standard operating procedure (used as synonym for all procedural documents)
TEAE	Treatment emergent adverse event
USP	United States Pharmacopeia
VAS	Visual analog scale
WPAI	Work Productivity and Activity Impairment

Système International d'Unités units and standard hematological and biochemical abbreviations are not listed.

### 3.2 Definition of terms

Term	Definition
Allocated subjects	Enrolled subjects who are allocated to IMP.
Applicable regulatory requirement(s)	Any law(s) and regulation(s) addressing the conduct of clinical trials of IMPs of the jurisdiction where the trial is conducted.
End of the trial	The trial-related end of the trial is defined as the date of last subject out. The subject-related end of trial is defined as date of last contact with the subject according to the protocol.
Enrolled subjects	Subjects who signed an informed consent form.
Enrollment failures	Enrolled subjects who were not allocated to IMP.
First subject allocated	First subject who was allocated to IMP.
First subject in	Date of first enrolled subject.
Investigational medicinal product	A generic term describing the preparation(s) under investigation in this trial, i.e., neridronic acid.
Last subject out	Date of last contact with the last subject according to the protocol.
Patient	Person under a physician's care for a particular disease or condition.
Screened subjects	Screened subjects are subjects undergoing screening. Screening is any activity concerning subjects who could potentially be enrolled into the trial before the informed consent form is signed.
Subject	Individual who participates in a clinical trial (healthy person or patient), either as recipient of an IMP or as an enrollment failure.
Treated subjects	Subjects with at least 1 administration of IMP.
Treatment completers	Treated subjects who completed IMP administration according to the protocol, i.e., subjects who received the full dose of all 4 planned infusions of IMP.

**Use of the terms “must” and “should”**

When “must” is used, the action/item is always mandatory. Non-compliance with this instruction constitutes a protocol deviation. When “should” is used, the action/item is recommended but not mandatory. Non-compliance with this instruction does not constitute a protocol deviation.

**4 ETHICS**

This trial will be conducted according to this protocol, the ethical principles that have their origin in the Declaration of Helsinki, good clinical practice (GCP), and applicable regulatory requirements.

This trial will be registered in public registries according to the applicable laws and requirements.

**4.1 Independent ethics committees or institutional review boards**

The relevant independent ethics committees (IECs) or institutional review boards (IRBs) for this trial will be provided with all documents required to fulfill their responsibilities. Any updates thereof will be provided according to GCP and applicable regulatory requirements.

Trial activities will only start when approval from the relevant IECs or IRBs is available.

Documentation of all involved IECs or IRBs will be maintained according to GCP and applicable regulatory requirements.

**4.2 Subject information and informed consent**

Before any trial-related procedure will be performed, freely given informed consent must be obtained.

The informed consent discussion, the information sheet (if used) and the informed consent form provided to subjects must adhere to GCP and applicable regulatory requirements. The informed consent discussion with the subject must be performed by the principal investigator or an appropriately trained delegate. The information sheet and/or informed consent form agreed with the sponsor must be used. Prior to use, these documents must be approved by the relevant IECs or IRBs.

Subjects must be informed as soon as possible if new information becomes available that may be relevant to their willingness to continue participation in the trial. The communication of this information must be documented.

Separate informed consent will be required from subjects participating in the bone biopsy assessment. Participation in the bone biopsy assessments will not be mandatory for participation in the trial.

Separate informed consent will be required from subjects participating in the imaging (DXA and MRI) assessments. Participation in these imaging evaluations is not mandatory for trial participation.

